6.3. Measures to Minimize Bias: Randomization and Blinding

6.3.1. Blinding and Randomization

This is an open-label, single-arm, non-randomized study therefore no procedures for blinding or randomization are applicable. All participants will receive the same study treatment.

6.3.2. Participant Numbering

A participant will be considered enrolled into the study as soon as he/she has signed the ICF. All participants who provide informed consent will be assigned a unique participant code by an Interactive Response Technology (IRT) system. Once a participant is enrolled, he/she will be identified only by the assigned participant code. Once assigned, a participant code must not be reused for any other participant.

The participant code will contain eight digits, corresponding to the country number, the site number and the participant's number according to chronological order (once having provided written informed consent).

6.3.3. Allocation of Study Treatment and Dispensing

Allocation of boxes of encorafenib to each participant will be controlled by the IRT system. Encorafenib will be allocated on Day 1 of each cycle during the treatment period. Returned encorafenib should not be re-dispensed.

Full information is described in the IRT Manual.

6.4. Study Treatment Compliance

As participants self-administer encorafenib at home, each participant will be reminded to bring back to the site any remaining encorafenib blisters and boxes (used or unused) from the previous cycle on Day 1 of the next cycle. Compliance with study treatment will be assessed on Day 1 of each cycle (from Cycle 2 onwards) by reviewing participant diary entries, accounting of returned study treatments and participant's interviews during the site visits and documented in the source documents and eCRF. Non-compliance from the prescribed dosage regimen should be recorded in the eCRF.

A record of the number of encorafenib capsules dispensed to and taken by each participant must be maintained and reconciled with study treatment and compliance records. The study treatment intake start and stop dates, including dates for study treatment delays and/or dose reductions will also be recorded in the eCRF.

6.5. Concomitant Medication and Therapeutic/Diagnostic Procedures

Any medication (including vaccines) other than study treatment (including non-prescription or prescription medicines or vitamins) taken in the period from 28 days before to the first administration of study treatment up to 30 days after the last dose of study treatment must be recorded. Any changes in dose of a medication during the study must also be recorded. The following information must be recorded in the eCRF:

- The name of the medication.
- The reason for prescription.
- The route of administration.
- The dose.
- The frequency.
- The duration (start date and end date).

The participant must be told to notify the study site about any new therapies and dietary supplements taken after the start of the study treatment.

Any therapeutic and diagnostic procedures (such as endoscopic examinations, diagnostics tests, ablation, surgical procedures, blood or platelet transfusions etc.) not planned by the study protocol must also be recorded. These procedures may be associated with events, in which case the condition that leads to the procedure must be reported in the appropriate section of the eCRF (adverse events, medical history). The following information must be noted in the eCRF:

- The name of the procedure.
- The indication.
- The duration (start date and end date).

Investigators should use caution when prescribing concomitant medications, as clinical experience with these compounds in participants with cancer is often limited. Investigators should contact the sponsor or designee when they are unsure whether a medication should be prescribed to a participant in the clinical study.

6.5.1. Authorized Medications, Therapeutic and Diagnostic Procedures

In general, the use of any concomitant medications deemed necessary for the care of the participant is permitted, unless otherwise specified. Additional information regarding concomitant medications is provided in the Investigator's Brochure.

Participants should be closely monitored for the occurrence of adverse events whilst taking permitted therapies requiring caution and/or action.

6.5.1.1. Authorized Therapies requiring Caution and/or Action

Participants should be closely monitored for the occurrence of adverse events whilst taking these therapies.

6.5.1.1.1. *Cytochrome P450 and Uridine 5'-diphospho-glucuronosyltransferase Substrates and Inhibitors*

Encorafenib is a reversible inhibitor of CYP2B6, CYP2C9, CYP3A4 and uridine 5'-diphospho-glucuronosyltransferase (UGT)1A1. It is also a time-dependent inhibitor of CYP3A4. Permitted medications to be used with caution in this study include those that are sensitive substrates of CYP2B6, CYP2C8, CYP2C9, CYP2C19, CYP3A4 (see Table 11 and Table 12) and UGT1A1 (see Table 13) or those substrates that have a narrow therapeutic index.

There is a potential for encorafenib to induce CYP3A4, which may reduce the effectiveness of hormonal contraception methods. At least one form of non-hormonal contraception is therefore required during participation in this study (see Section 5.3.1). Caution should also be exercised in participants receiving concomitant treatment with other drugs that are substrates of CYP3A4 as the efficacy of these drugs could be reduced when administered with encorafenib.

Encorafenib has been identified in vitro to be metabolized by CYP3A4 and to a lesser extent by CYP2C19. The use of strong inhibitors of CYP3A4 is prohibited (see Section 6.5.2). Concomitant use of moderate CYP3A4 inhibitors (see Table 14) while on study should be avoided. If use of moderate CYP3A4 inhibitors is unavoidable and no alternatives are available, short-term use (≤ 30 days) following discussion with the sponsor may be permitted with accompanying dose reduction to one-half of the encorafenib dose before use of moderate CYP3A4 inhibitors (or as close as can be achieved without exceeding the target dose). The encorafenib dose that was taken before initiating the CYP3A4 inhibitor may be resumed after the inhibitor has been discontinued for three to five elimination half-lives. Strong inhibitors of CYP2C19 should be used with caution when coadministered with encorafenib.

6.5.1.1.2. *Transporter Substrate and Inhibitors*

In vitro data showed that encorafenib is a substrate of the transporter P-glycoprotein (P-gp) and a breast cancer resistance protein (BCRP) inhibitor. Use of medications that are known to inhibit or induce P-gp or BCRP should be used with caution (see Table 15). Encorafenib is also a potent inhibitor of the renal transporters, organic anionic transporter (OAT)1, OAT3 and organic cationic transporter (OCT)2 and the hepatic transporter organic anion-transporting peptide (OATP1)B1 and OATP1B3. The co-administration of drugs that are known to be sensitive or narrow therapeutic index substrates of BCRP, P-gp, OAT1, OAT3, OCT2, OATP1B1 and OATP1B3 should be used with caution (see Table 16).

6.5.1.1.3. *Drugs with a Conditional or Possible Risk to Prolong the QT Interval and/or Induce Torsade de Pointes*

Investigators should use caution when administering encorafenib with concomitant medications with a known, conditional or possible risk to prolong the QT interval and/or induce Torsade de Pointes (see Table 17). Participants receiving such medications must be carefully monitored for potentiation of toxicity due to any individual concomitant medication and may require dose titration of the concomitant medication.

6.5.2. **Prohibited Medications and Therapeutic/Diagnostic Procedures**

The following therapies are prohibited during screening and the Treatment Period (unless otherwise noted). There are no prohibited therapies during the post-treatment Follow-up Period. None of the concomitant therapies and therapeutic/diagnostic procedures listed below are allowed during the treatment phase:

- Anticancer agents such as cytotoxic chemotherapy small-molecule targeted agents, biological agents, immune response modifiers or hormonal therapy.
- Local therapies which could interfere with treatment (e.g. surgical excision or ablation of lesions are not permitted without sponsor approval).
- Investigational drugs (other than study treatments) and devices.
- Radiation therapy (not including palliative radiotherapy at focal sites that covers $\leq 10\%$ of the bone marrow reserve). Calculation of the percentage of active bone marrow reserve can be performed using information in **Table 6 [Hindorf, 2010]**.

Note: The participant must have clear measurable disease outside the radiated field.

Note: Radiation therapy to a symptomatic solitary lesion or to the brain may be considered on a case-by-case basis after consultation with the sponsor's medical monitor.

Note: Administration of palliative radiation therapy will be considered clinical progression.

- Herbal preparations/medications. Participants should stop using herbal medications (including use of St. John's Wort [*hypericum perforatum*] and traditional Chinese medicine

susceptible to be a moderate or strong inhibitor or inducer of CYP3A4/5) 7 days before the first dose of study treatment.

- Concomitant systemic strong CYP3A4 inhibitors or moderate/strong inducers which are likely to significantly increase or decrease respectively encorafenib exposure (listed in Table 18).

Table 6: The percentage of total red marrow present at different skeletal sites in a healthy adult

Skeletal site	Percentage of red marrow
Cranium	7.6
Mandible	0.8
Scapulae	2.8
Clavicles	0.8
Sternum	3.1
Ribs	16.1
Cervical vertebrae	3.9
Thoracic vertebrae	16.1
Lumbar vertebrae	12.3
Sacrum	9.9
Os coxae	17.5
Femora, upper half	6.7
Femora, lower half	0
Tibiae, fibulae, patellae	0
Ankle and foot bones	0
Humeri, upper half	2.3
Humeri, lower half	0
Ulnae, radii	0
Wrist and hand bones	0

If another therapy and/or therapeutic/diagnostic procedure has to be prescribed in the interests of the participant's health, the decision to discontinue the participant from the study should be taken by the investigator.

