Encorafenib will be orally self-administered. A fixed-flat dose of 300 mg PO encorafenib will be administered QD. Encorafenib should be taken daily in the morning at approximately the same time (\pm 2 hours) every day without regard to food. If a participant vomits at any time after dosing, the dose should not be re-administered. Doses of encorafenib that are omitted for adverse events or any other reason should not be made up during the day, or at the end of the dosing period.

The first dose of encorafenib will be taken on Cycle 1 Day 1 and will then be continuously self-administered in 28-day cycles until death, disease progression, one of the other criteria for study treatment discontinuation is met (see Section 7.1) or the participant is lost to follow-up (see Section 7.3). On Day 1 of each cycle the encorafenib dose will be administered at the study site.

Lifestyle considerations in relation to dosing are detailed in Section 5.3. There are no restrictions on dosing in relation to the timing of meals.

Participants will receive a diary to document self-administration of encorafenib to include the dose, date of dosing (and time if applicable), if the participant vomited after dosing, if any doses were missed and the reason for the missed dose. One diary will be provided per cycle. On the days when encorafenib is administered at the study site, these details will be recorded in the eCRF by the study site personnel.

Management of dose modifications (including dose interruptions and retreatment) are detailed in Section 6.6.

Continuing study treatment beyond disease progression for any participant is only to be considered under special circumstances when it is believed that the participant may clinically benefit from continued treatment beyond progression. If it is judged by the investigator (in consultation with the sponsor) to be in the best interest of the participant, the participant may remain on study treatment as long he/she continues to benefit from the study treatment according to the investigator's assessment. Special circumstances can be defined by e.g. mixed responses and appearance of new brain metastases (only) which is treatable with stereotactic radiotherapy or surgery but does not require whole brain radiotherapy.

Treatment beyond progression is not allowed in the following cases:

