7.1.2. Permanent Study Treatment Discontinuation

Study treatment is to be administered until any of the following criteria for permanent discontinuation is met:

- Disease progression, as defined by Response Evaluation Criteria in Solid Tumors (RECIST) Version 1.1 (continuation of treatment beyond progression is permitted in special circumstances, see **Section 6.1**).

- Clinical progression, as determined by the investigator in the absence of radiographic progression.
- Withdrawal of consent. Participants may choose to withdraw consent to continue study treatment but remain in the study to be followed for safety and disease progression. In this case, follow-up data will continue to be collected for this participant. Withdrawal of consent for study treatment may occur at any time without penalty of jeopardizing their healthcare or loss of benefits to which they are otherwise entitled. Participants who withdraw consent to study treatment and follow-up, will no longer receive study treatment or followed up within this study.
- Unacceptable adverse events or failure to tolerate study treatment:
 - Grade 4 or life-threatening adverse event as outlined in Appendix 10.4 (except with approval from the sponsor's medical monitor)
 - Toxicity requiring more than the allowed number of dose reductions for encorafenib, (see **Table 7**).
 - Occurrence of an adverse event that is related to study treatment and compromises the participant's ability to continue study-specific procedures according to investigator's judgement or is considered to not be in the participant's best interest. The medical monitor or delegate should immediately be informed by phone or e-mail and a report explaining the discontinuation will be forwarded to him/her as soon as possible.
- Initiation of subsequent anticancer therapy.
- Participant is non-compliant with study procedures or study treatment that in the judgment of the investigator or sponsor renders the participant unsuitable.
- Significant protocol deviation that, in the opinion of the investigator and/or sponsor, renders the participant unsuitable for further study treatment administration.
- Participant has missed >4 weeks (i.e., 28 consecutive days) of dosing (see Section 7.1.1).
- Participant becomes pregnant or begins breastfeeding.
- Participant is lost to follow-up.
- Defined end of the study (see Section 4.4)

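### Permitted on-treatment focal palliative radiotherapy is also classed as clinical progression, a criterion for stopping the drug, and no rule says which governs

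*Protocol*

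**What the plan says.** Protocol Section 6.5.2 prohibits radiation therapy, but its exception reads "not including palliative radiotherapy at focal sites that covers" no more than 10% of the bone marrow reserve. Table 6 is supplied for calculating that share. A condition follows: "Note: The participant must have clear measurable disease outside the radiated field". A separate note says "Radiation therapy to a symptomatic solitary lesion or to the brain may be considered on a case-by-case basis", after consultation with the sponsor's medical monitor. The focal exception carries no consultation requirement. The last note under the same bullet is unqualified: "Note: Administration of palliative radiation therapy will be considered clinical progression".

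Protocol Section 7.1.2 opens: "Study treatment is to be administered until any of the following criteria for permanent discontinuation is met". One of its bullets is "Clinical progression, as determined by the investigator in the absence of radiographic progression". The allowance for continuing beyond progression sits in a different bullet, the one for RECIST progression.

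Protocol Section 6.1 lets the investigator, in consultation with the sponsor, continue treatment beyond disease progression in special circumstances. Its examples are mixed responses and "appearance of new brain metastases (only) which is treatable with stereotactic radiotherapy or surgery", provided whole brain radiotherapy is not required.

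SAP Section 6.7.2 counts radiotherapy among the concomitant antineoplastic therapies, and SAP Section 5.2 tabulates the reason for treatment discontinuation.

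**The concern.** The exception and its condition look forward to a participant who stays on treatment, since measurable disease outside the field matters most if response is still being followed. The note then gives the same act a label that Section 7.1.2 treats as a reason to stop for good. There is a second mismatch: the note applies the label automatically, while Section 7.1.2 leaves clinical progression to the investigator's determination.

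Two investigators with the same participant could therefore each follow the protocol and do opposite things. One relies on the exception and continues dosing. The other applies the note and Section 7.1.2, stops, and records clinical progression. In a study of up to six evaluable participants at two or three sites, one such difference is visible in the exposure and discontinuation summaries. If it falls early in Cycle 1, it can also decide whether that participant counts towards the DLT rate.

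**Working it through.** The documents state no figure to reproduce. The check compares the texts and adds two short calculations.

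**Texts side by side, for focal non-brain palliation during treatment**

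| Source (Protocol) | Effect on the participant |
|---|---|
| 6.5.2, exception | Permitted at 10% of marrow or less; no consultation required |
| 6.5.2, closing note | Classed as clinical progression, automatically |
| 7.1.2, clinical-progression bullet | Permanent discontinuation if the investigator determines clinical progression; no exception attached |
| 7.1.2, RECIST bullet | Continuation possible, by reference to 6.1 |
| 6.1 | Discretionary continuation with sponsor consultation; focal radiotherapy outside the brain is not among the examples |

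No line says whether permitted focal radiotherapy ends treatment. The SAP's concomitant-radiotherapy listing fits continued dosing but does not settle the matter.

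**Does the exception cover real cases?** Several whole sites in Table 6 fall at or below 10%: sacrum 9.9%, cranium 7.6%, upper femora 6.7%, cervical vertebrae 3.9%. It does.

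**When would a stop change DLT evaluability?** Inputs: 300 mg daily for 28 days (SAP Section 5.6.1), and evaluability through a DLT, or through a completed cycle with at least 75% dose intensity (Protocol Sections 4.1.1 and 9.2).

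- Planned Cycle 1 dose: 28 × 300 = 8400 mg.
- Threshold: 0.75 × 8400 = 6300 mg, and 6300 / 300 = 21 full doses.
- Illustration, drug stopped on Day 14: 13/28 = 46.4% if that day's dose is not taken, 14/28 = 50% if it is. Both are below 75%.
- Stopped after 21 full doses: 21/28 = 75%, so the dose condition is met. What remains is the completed cycle, which Protocol Section 9.3 and SAP Section 4.2 express as at least 28 days of observation after the first dose.
- With a DLT in Cycle 1: evaluable whatever the dose intensity.

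A participant without a DLT who stops before these conditions are met is non-evaluable and, under the Synopsis, replaced. The same participant kept on drug through Day 28 with at least 6300 mg is counted.

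**The case against.** The strongest reply is that a coherent chain can be built. Permitted radiotherapy is not a prohibited-therapy deviation, it is labelled progression, and continuation is then decided under Section 6.1. That section speaks of disease progression generally, its examples are only examples, and one of them involves stereotactic radiotherapy. Investigator judgement, medical-monitor consultation for brain or solitary-lesion radiation, and the small number of sites all narrow the room for divergence. Entry criteria (ECOG 0 or 1, life expectancy of at least 3 months, no symptomatic brain metastases) make early palliation less likely, and Protocol Section 8.2 says efficacy is not formally assessed.

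Much of this stands, and it rules out some stronger conclusions that a reader might draw:

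- *The permission is void because every permitted use ends treatment.* Not supported. Section 6.5.2 also governs screening, where no study treatment has begun (exclusion criterion 3c separately requires palliative radiation to be complete 7 days before the first dose), and Section 6.1 may cover some on-treatment cases.
- *Anyone irradiated and stopped in Cycle 1 falls below 75%.* Not supported after 21 full doses.
- *One third of the first-stage denominator is lost.* Not supported. Replacement restores three evaluable participants, and the DLT count changes only if the replacement's outcome differs from the one that the replaced participant would have had.
- *The SAP needs a radiotherapy rule for the Dose-Determining Set.* Not supported. Dose intensity, 28-day observation or a DLT already fix membership.

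The chain itself, however, is written nowhere. Section 7.1.2 ties the continuation route to RECIST progression only, and the focal exception requires no consultation while Section 6.1 does. The gap for focal non-brain palliation remains.

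**Conclusion.** The conflict is real but narrow. For permitted focal palliative radiotherapy outside the brain, given on treatment, the protocol supports both continuing and permanently stopping encorafenib, and nothing in either document resolves it. The certain consequences are for treatment duration, exposure and the recorded reason for discontinuation. The effect on the primary endpoint is conditional: it needs radiotherapy in Cycle 1, a stop before the evaluability conditions are met, and no DLT, and the participant is then replaced. The documents give no frequency for on-treatment palliation, so no rate is claimed. The conclusion rests on reading the note as unqualified, as written, and takes no position on which clinical rule is right.

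**What to change.** Reconcile four pieces of Protocol text: the Section 6.5.2 exception, its closing note, the Section 6.1 provision on treatment beyond progression, and the clinical-progression bullet of Section 7.1.2. One rule, chosen by the sponsor, should state whether permitted on-treatment palliative radiotherapy triggers discontinuation. It should also say whether the clinical-progression label is automatic or left to the investigator, and whether Section 6.1 applies. The reason for discontinuation summarised under SAP Section 5.2 should then be coded to match. The definition of the Dose-Determining Set can stay as it is. The cost is a wording clarification and a coding note, with no extra participants or procedures.

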6.6. Dose Modification

Participants will be monitored for adverse events throughout the study. The severity of adverse events will be graded according to National Cancer Institute Common Terminology Criteria for Adverse Events NCI CTCAE Version 4.03 [NCI CTCAE 2010].

If a participant develops toxicity, the dose should be modified as outlined in Appendix 10.4. This table include criteria for interruption, reduction and discontinuation of study treatment. All dose modifications should be based on the worst preceding toxicity. All dosing interruptions and modifications must be recorded in the eCRF.

Individual decisions regarding dose modifications should be made using appropriate clinical judgment, considering relatedness of the adverse event to the study treatment and the participant's underlying condition. Adverse events that have a clear alternative explanation or are transient (≤ 72 hours) abnormal laboratory values without associated clinically significant signs or symptoms may be exempt from dose reduction rules. The investigator should follow the study site supportive guidelines for the management of these toxicities and prophylactic measures.

